4.1.6 Study Specific Ophthalmologic Exams

An age-appropriate ophthalmologic examination that avoids any sedation should be performed by an ophthalmologist at baseline, at the end of Cycle 1, and every 12 weeks thereafter, while on study. This includes a Snellen examination (if age appropriate as determined by the investigator). The examination must include a funduscopy evaluation to rule out retinal vein occlusion (RVO) and retinal pigment epithelial detachment (RPED), can be dilated or non-dilated at discretion of ophthalmologist and can be accomplished using imaging with a non-mydratic fundus camera.

4.2 Cycle 1

4.2.1 Therapy Delivery Map – Cycle 1 This therapy Delivery Map (TDM) relates to Cycle 1. Each cycle lasts 28 days.
	
_____
 
Patient COG ID number
 
_____
 
DOB

--	---

Criteria to start each cycle are listed in [Section 3.2.5](#). Treatment details are provided in [Section 4.2.3](#). This treatment delivery map is **two (2)** pages in length.

DRUG	ROUTE	DOSAGE	DAYS	IMPORTANT NOTES
Trametinib Do not use commercial supply	PO	Age-based dosing: < 6 years= 0.032 mg/kg/dose ≥ 6 years = 0.025 mg/kg/dose Max dose= 2 mg	Daily	See Appendix II for tablet formulation dosing nomogram.

Enter Cycle #: _____ Ht _____ cm Wt _____ kg BSA _____ m²

Date Due	Date Given	Day	Trametinib mg	Studies
			Enter calculated dose above and actual dose administered below	
		1	_____ mg	a-f, (g-p)*, q, r [%]
		2	_____ mg	
		3	_____ mg	
		4	_____ mg	d
		5	_____ mg	
		6	_____ mg	
		7	_____ mg	
		8	_____ mg	a, d, e
		9	_____ mg	
		10	_____ mg	
		11	_____ mg	d
		12	_____ mg	
		13	_____ mg	
		14	_____ mg	
		15	_____ mg	a, d, e, q
		16	_____ mg	
		17	_____ mg	
		18	_____ mg	d
		19	_____ mg	
		20	_____ mg	
		21	_____ mg	
		22	_____ mg	a, d, e
		23	_____ mg	
		24	_____ mg	
		25	_____ mg	d
		26	_____ mg	
		27	_____ mg	
		28	_____ mg	(a, d, e, g-m, r) [#]
		29	
[#]Following the completion of Cycle 1 therapy, perform the disease evaluations a, d, e, g-m, and r within 3 days, and prior to the start of the next cycle.
 
Please continue onto the next cycle no later than 14 days from the end of the previous cycle. The next cycle starts on Day 29 or when starting criteria are met (see Section 3.2.5), whichever occurs later.
	

See [Section 5.0](#) for Dose Modifications for Toxicities and the COG Member website for Supportive Care Guidelines.

4.2.2 Required Observations in Cycle 1

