***For Day 1 observations, g- p samples may be collected up to 14 days prior to the start of therapy.**

%JMML panel for mutant allele burden may be collected up to 14 days prior to the start of therapy if sent as a correlative biology study on this trial or up to 30 days prior to the start of therapy if the same test was ordered as fee-for-service and processed at UCSF.

- a. Physical exam (including VS with triplicate BPs), and adverse events
- b. Concomitant medications
- c. Performance status
- d. CBC, differential, platelets (see [Section 7.2](#) for details regarding Central Review).
- e. Electrolytes including Ca^{2+} , Mg^{2+} , and PO_4 , BUN and creatinine, creatine kinase bilirubin (total and direct), AST, and ALT
- f. Dermatologic exam. Performed by the treating physician (or dermatologist, at the discretion of the investigator). If possible, the same physician should perform each exam throughout the study. Photographs of suspect lesions at baseline are recommended. Photographs and/or biopsies of any new or changing lesions recommended at subsequent on-study visits
- g. An age-appropriate ophthalmologic examination with a funduscopy evaluation that avoids any sedation to be performed by an ophthalmologist at baseline. This includes a Snellen examination (if age appropriate as determined by the investigator). See [Section 4.1.6](#)
- h. Peripheral blood smear (See [Section 7.2](#) for details regarding Central Review)
- i. BMA/clot section or biopsy and aspirate smear (see [Section 7.2](#) for details regarding Central Review)
- j. BMA cytogenetics and FISH (It is recommended that cytogenetics/FISH be performed by a COG-approved laboratory)
- k. For patients that consent, collect bone marrow for Genomic, Epigenomic, and Functional assays (see [Section 7.3.3](#))
- l. Echocardiogram or MUGA
- m. ECG
- n. CSF for cell count, cytospin (lumbar puncture only required if clinical suspicion of CNS involvement)
- o. Pregnancy test. Female patients of childbearing potential require a negative pregnancy test
- p. Imaging (CT or MRI) of chloroma (if present)
- q. For patients that consent, collect peripheral blood for Pharmacokinetic and Pharmacodynamic studies (see [Section 7.4.1](#))
- r. Peripheral blood sample for the JMML panel using mutant allele burden (see [Section 7.3.1](#))

This listing only includes evaluations necessary to answer the primary and secondary aims. OBTAIN OTHER STUDIES AS REQUIRED FOR GOOD CLINICAL CARE.

Comments

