
4.3.1 Therapy Delivery Map – Cycle 2 This therapy Delivery Map (TDM) relates to Cycle 2. Each cycle lasts 28 days.
	
_____
 
Patient COG ID number
 
_____
 
DOB

--	---

Criteria to start each cycle are listed in [Section 3.2.5](#). Extensive treatment details are in [Section 4.3.3](#).
This treatment delivery map is **two (2)** pages in length.

DRUG	ROUTE	DOSAGE	DAYS	IMPORTANT NOTES
Trametinib Do not use commercial supply	PO	Age-based dosing: < 6 years= 0.032 mg/kg/dose ≥ 6 years = 0.025 mg/kg/dose Max dose= 2 mg	Daily	See Appendix II for tablet formulation dosing nomogram.

Enter Cycle #: _____ Ht _____ cm Wt _____ kg BSA _____ m²

Date Due	Date Given	Day	Trametinib mg	Studies
Enter calculated dose above and actual dose administered below				
		1	mg	a-f
		2	mg	
		3	mg	
		4	mg	
		5	mg	
		6	mg	
		7	mg	
		8	mg	d
		9	mg	
		10	mg	
		11	mg	
		12	mg	
		13	mg	
		14	mg	
		15	mg	a, d, e
		16	mg	
		17	mg	
		18	mg	
		19	mg	
		20	mg	
		21	mg	
		22	mg	d
		23	mg	
		24	mg	
		25	mg	
		26	mg	
		27	mg	
		28	mg	(d, e, g-l) [#]
		29	[#] Following the completion of Cycle 2 therapy, complete observations d, e, g-l within 3 days, and prior to the start of the next cycle. The next cycle starts on Day 29 or when starting criteria are met (see Section 3.2.5), whichever occurs later. Please continue onto the next cycle no later than 14 days from the end of the previous cycle.	

See [Section 5.0](#) for Dose Modifications for Toxicities and the COG Member website for Supportive Care Guidelines.

4.3.2 Required Observations in Cycle 2

- a. Physical exam (including VS) and adverse events
- b. Concomitant medications
- c. Performance status
- d. CBC, differential, platelets (see [Section 7.2](#) for details regarding Central Review)
- e. Electrolytes including Ca²⁺, Mg²⁺, and PO₄, BUN and creatinine, creatine kinase, Total and direct bilirubin, AST, and ALT
- f. Dermatologic exam. Performed by the investigator (or dermatologist, at the discretion of the investigator). If possible, the same physician should perform each exam throughout the study. Photographs of suspect lesions at baseline are recommended with photographs and/or biopsies of any new or changing lesions recommended at subsequent on-study visits
- g. Peripheral blood smear (see [Section 7.2](#) for details regarding Central Review)
- h. BMA/clot section or biopsy and aspirate smear (see [Section 7.2](#) for details regarding Central Review)

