4.4 Cycle 3 and All Subsequent Cycles

4.4.1 Therapy Delivery Map – All Subsequent Cycles This therapy Delivery Map (TDM) relates to all subsequent cycles. Each cycle lasts 28 days. Use a copy of this page once for each cycle (please note cycle number below).
	
_____ Patient COG ID number
 
_____ DOB

--	---

Criteria to start each cycle are listed in [Section 3.2.5](#). Treatment details are in [Section 4.4.3](#).

This therapy delivery map is **two (2)** pages in length.

DRUG	ROUTE	DOSAGE	DAYS	IMPORTANT NOTES
Trametinib Do not use commercial supply	PO	Age-based dosing: < 6 years= 0.032 mg/kg/dose ≥ 6 years = 0.025 mg/kg/dose Max dose= 2 mg	Daily	See Appendix II for tablet formulation dosing nomogram.

Enter Cycle #: _____ Ht _____ cm Wt _____ kg BSA _____ m²

Date Due	Date Given	Day	Trametinib mg	Studies
			Enter calculated dose above and actual dose administered below	
		1	_____ mg	a-g
		2	_____ mg	
		3	_____ mg	
		4	_____ mg	
		5	_____ mg	
		6	_____ mg	
		7	_____ mg	
		8	_____ mg	
		9	_____ mg	
		10	_____ mg	
		11	_____ mg	
		12	_____ mg	
		13	_____ mg	
		14	_____ mg	
		15	_____ mg	
		16	_____ mg	
		17	_____ mg	
		18	_____ mg	
		19	_____ mg	
		20	_____ mg	
		21	_____ mg	
		22	_____ mg	
		23	_____ mg	
		24	_____ mg	
		25	_____ mg	
		26	_____ mg	
		27	_____ mg	
		28	_____ mg	h, i [#] , j, k
		29	[#] See note on page 2 of TDM regarding observation i. Following completion of the cycle, the next cycle starts on Day 29 or when starting criteria are met (see Section 3.2.5), whichever occurs later. Please continue onto the next cycle no later than 14 days from the end of the previous cycle.	

See [Section 5.0](#) for Dose Modifications for Toxicities and the COG Member website for Supportive Care Guidelines.

4.4.2 Required Observations in All Subsequent Cycles**Collect observations beginning in Cycle 3.**

- a. Physical exam (including VS) and adverse events
- b. Concomitant medications
- c. Performance status
- d. CBC, differential, platelets
- e. Electrolytes including Ca^{2+} , Mg^{2+} , and PO_4 , BUN and creatinine, creatinine kinase, Total and direct bilirubin, AST, and ALT

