APPENDIX III: RESPONSE CRITERIA FOR PATIENTS WITH JMML

Table 1: Variables for evaluation of response to therapy in JMML

Variables for Response	Definition of response			Definition of disease progression or relapse (applicable to all patients)	
	Assessment of CR and PR is feasible if the following are present before therapy	Requirement for CR for each variable (vCR)	Requirement for PR for each variable (vPR)	Requirement for PD for each variable (vPD)	
Clinical variables	1) WBC count	>20 × 10 ⁹ /L	3.0 – 15.0 × 10 ⁹ /L	Decreased by ≥50% over pretreatment but still >15 × 10 ⁹ /L	Increase by ≥50% and ≥20 × 10 ⁹ /L
	2) Myeloid and erythroid precursors and blasts in PB*	≥ 5%	0-1%	Decreased by ≥50% over pretreatment but still ≥ 2%	Increase from the baseline: < 5%: ≥ 50% increase and ≥ 5% ≥ 5%: ≥ 50% increase of total % of myeloid and erythroid precursors and blasts
	3) Platelet count	<100 × 10 ⁹ /L	>100 × 10 ⁹ /L	For patients starting with ≥ 20 × 10 ⁹ /L platelets: absolute increase of ≥ 30 × 10 ⁹ /L For patients starting with < 20 × 10 ⁹ /L platelets: increase by ≥ 100% and > 20 × 10 ⁹ /L	Development of transfusion dependency or if patients have the baseline of the platelet count of ≥30 × 10 ⁹ /L, decrease by ≥50% and <100 × 10 ⁹ /L
	4) BM blasts	≥5%	<5%	Decreased by ≥50% over pretreatment but still ≥5%	Increase from base line; < 5%: ≥ 50% increase and ≥ 5% ≥ 5%: ≥ 50% increase of BM blasts
	5) Spleen size				
	a) Clinical evaluation or	≥2 cm under the costal margin	No splenomegaly	50% decrease by cm under the costal margin	Increase by ≥100% if baseline <4cm from under the costa margin ≥50% if baseline 5-10cm >30% if baseline >10 cm
b) Sonography	Length of spleen ≥ 150% of upper limit of normal range	No splenomegaly	>25% decrease by length, but still splenomegaly	Increase by ≥25% of length	
6) Extramedullary disease#	Extramedullary leukemic infiltration	No evidence of extramedullary leukemic infiltration in any organ	-	Worsening or new lesions of extramedullary leukemic infiltration	
7) Cytogenetic response	Somatic cytogenetic abnormality detected	Normal karyotype	-	Reappearance or additional acquirement of cytogenetic abnormalities	
8) Molecular response	Somatic genetic anomalies detected**	Absence of somatic genetic anomalies	-	Reappearance or additional acquirement of JMML-specific somatic gene abnormalities	

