9) Chimerism response (only for patients after HSCT)	>15% autologous cells after allo-HSCT	Complete donor chimerism	-	50% increase and >5% increase of autologous cells and >5%	

CR: complete response, PR: partial response, PD: progressive disease, WBC: white blood cell, PB: peripheral blood, BM: bone marrow

*Myeloid precursors include promyelocytes, myelocytes, and metamyelocytes. The myeloid and erythroid precursors and blasts in PB are given as % of the total nucleated cells in PB (WBC including erythroblasts).

**in *NF-1*, *PTPN11*, *NRAS*, *KRAS*, *RRAS2*, or *CBL*, thus the mutation are thought to be initiating. In patients with germ-line *NF-1*, *PTPN11* or *CBL* mutation, only acquired mutations can be evaluated for response and relapse after therapy. The germ-line mutation remains even if patients achieved complete molecular response. The molecular response will be determined using the “JMML Mutant Allele Burden” assay.

Criteria for progression including WBC, platelet count and spleen size cannot be used in the setting of an active infection.

#Extramedullary disease includes infiltration of skin, lung, and very rarely cranial nerves or central nervous system.

Table 2: Definition of response following therapy other than HSCT in JMML

Clinical remission status: parameter 1-6 of table 1		Genetic remission status: parameter 7-9 of table 1	
Clinical complete remission (cCR)	Patient fulfills the criteria of CR of all applicable clinical variables 1-6 of table 1 The response parameters must be maintained for at least 4 weeks.	Genetic complete remission (gCR)	Defined if the patient shows a normal karyotype and absence of acquired mutations in PTPN11 , NF-1 , NRAS , KRAS , or CBL .
Clinical partial remission (cPR)	Defined if the patient does not fulfill the criteria of cCR, but vPR was achieved in at least one of clinical variables (1 – 6) and none of clinical variables showed vPD.	-	-
Clinical stable disease (cSD)	Defined if the patient does not fulfill the criteria of cCR and cPR, but none of the parameter showed vPD.	Genetic stable disease (gSD)	Defined if the patient does not fulfill the criteria of gCR, but none of the genetic parameters (7-9) showed vPD.
Clinical progressive disease (cPD)	Defined if any of the parameters 1-6 showed vPD.	Genetic progressive disease (gPD)	Defined if any of the parameters 7-9 showed vPD.

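### Read literally, Appendix III gives no clinical partial remission for normalising a variable, so a larger improvement can score SD where a smaller one scores PR

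*Combined protocol and SAP*

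**What the plan says.** Appendix III, Table 2 defines three outcomes for a patient without progression in any clinical variable.

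- **cCR:** vCR in every applicable clinical variable, with the condition "The response parameters must be maintained for at least 4 weeks".
- **cPR:** cCR is not met, but "vPR was achieved in at least one of clinical variables".
- **cSD:** neither of these.

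Table 1 sets the bands. For WBC, peripheral-blood precursors and marrow blasts, vPR is "Decreased by ≥50% over pretreatment but still" above 15, at least 2% and at least 5% respectively. The vCR ranges are 3.0–15.0, 0–1% and below 5%. For spleen by sonography, vPR is more than a 25% "decrease by length, but still splenomegaly", and vCR is no splenomegaly. Extramedullary disease has a vCR but no vPR. Platelets and palpable spleen have a vPR without an upper cap.

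Section 10.2 maps genetic stable disease (gSD) with cCR or cPR to PR, and gSD with cSD to SD. Section 9.3 counts only PR or CR as response, taking the best response over 12 cycles before progression.

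**The concern.** For four variables vPR and vCR cannot both hold, and cPR asks for vPR. A gSD patient is therefore SD if all of the following are true:

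- the patient normalises one of these variables but does not reach cCR (which includes all variables normal for under 4 weeks);
- there is no vPR in another variable or at an earlier assessment;
- there is no progression in any variable.

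A smaller fall in the same variable would have been PR. Nothing in Sections 9.3 or 10.2 or in Appendix III says that vCR satisfies the vPR requirement.

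With gSD, cPR versus cSD decides responder status for the primary endpoint. Section 2.2.1 reports that mutant cells persisted under MEK inhibition in mice, so gSD may be common here. Patients with genetic complete remission are unaffected, because gCR with cSD is already CR.

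**Working it through.** **1. Literal scoring, gSD throughout.**

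| Change from baseline | Variable level | Overall |
|---|---|---|
| WBC 40 to 18 (−55%), spleen 6 to 4 cm (−33%), platelets 60 to 75 (+15) | WBC vPR; others neither | PR |
| WBC 40 to 10 (−75%), the rest identical | WBC vCR; others neither | SD |
| WBC 28 to 12 (−57%), marrow blasts 8% to 3% (−62.5%), platelets 85 to 105 (+20), nothing else applicable, held 4 weeks | all vCR, none vPR | PR (via cCR) |
| The same, held under 4 weeks | all vCR, none vPR | SD |

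**2. Where a vPR band exists.** A 50% fall that stays above the vCR range needs:

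- WBC: baseline/2 > 15, so baseline above 30. Response is assessable from above 20, so the band is empty for baselines above 20 up to 30.
- Marrow blasts: baseline/2 ≥ 5%, so baseline of 10% or more. The band is empty from 5% to below 10%.
- Peripheral-blood precursors: from 5%, the band is 2% to 2.5% or wider, so it always exists.
- Sonographic spleen: from 150% of the upper limit, a 25% fall gives 112.5%. A band always exists if splenomegaly means above that limit.

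Where the band is empty, the patient cannot pass through vPR on the way to normal. There is then no inversion within that variable, only no cPR credit for normalising it. Extramedullary disease is in the same position.

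Platelets can be vCR without vPR only from a baseline above 70 (a rise below 30 that ends above 100). Palpable spleen has no inversion if its 50% decrease is read as at least 50%. No spleen sonography appears in the required observations, so that arm matters only where a site uses it.

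**3. Can passing through vPR rescue the WBC case?** Assume a steady exponential fall and that mid-cycle counts are used for response. The band opens after one half-time and closes at WBC 15, so it lasts log2(baseline/30) half-times: 0.222, 0.415, 1.0 and 1.415 for baselines 35, 40, 60 and 80.

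Cycle 1 CBCs fall on Days 1, 4, 8, 11, 15, 18, 22, 25 and 28, so gaps are at most 4 days. If the band is crossed in Cycle 1, capture is guaranteed once the half-time reaches 4/0.222 = 18 days, 4/0.415 = 9.6, 4/1.0 = 4.0 or 4/1.415 = 2.8.

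These are sufficient worst-gap bounds. On the actual CBC days many shorter half-times are also caught: about 63% of an even spread from 2 to 18 days (baseline 35) and about 72% from 2 to 9.6 days (baseline 40).

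Cycle 2 has CBCs on Days 1, 8, 15, 22 and 28. From Cycle 3 there is one per cycle, and the worst-gap bounds over 28 days become 126, 67, 28 and 20 days. Marrow is taken after Cycles 1 and 2 and then only conditionally in odd cycles (4.4.2, item i).

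**4. Design figures.** For the Section 9.2 rule, early stopping is (1 − p)^10. Success is the sum over x ≥ 1 first-stage responses of P(x of 10) × P(at least 3 − x of the next 10). This reproduces the plan: at 5%, success 0.069 and early stopping 0.599; at 25%, 0.882 and 0.056.

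Let m be the share of responders lost by the literal wording. The documents give no value, so all m are assumptions.

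| m | 0.25(1 − m) | Power | Wrong stage-1 stop | 0.05/(1 − m) | Type I error, wider rule |
|---|---|---|---|---|---|
| 0 | 0.250 | 0.882 | 0.056 | 0.0500 | 0.069 |
| 10% | 0.225 | 0.829 | 0.078 | 0.0556 | 0.088 |
| 20% | 0.200 | 0.759 | 0.107 | 0.0625 | 0.115 |
| 30% | 0.175 | 0.669 | 0.146 | 0.0714 | 0.154 |
| 40% | 0.150 | 0.560 | 0.197 | 0.0833 | 0.211 |

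The power columns apply if 25% is the rate under the ordered reading. The last two columns apply if the 5% null was set for the literal wording.

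**The case against.** PR and CR are ordered grades, so a scorer may naturally take an achieved vPR to mean at least vPR, and then nobody is lost. Section 10.2 credits the criteria to an international consensus panel, whose own handling of this point is not in the documents. That reading is plausible but unwritten. Since Table 1 caps vPR for some variables and not for others, two scorers could classify the same patient differently.

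The literal SD also needs several conditions together, and best response over 12 cycles with frequent early CBCs removes some cases. This stands. A reader might infer from the half-time limits that faster WBC falls are necessarily missed; the CBC calendar does not support that. Protection is weakest where the vPR band is empty, for baseline WBC just above 30, for marrow blasts, and for late responses, which Section 2.7 gives as the reason for Amendment #3.

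A reader might also infer a definite loss of power. Section 9.2 defines the endpoint by the Section 10.2 criteria and then states 5% and 25%, so both can fairly be read as rates under the wording as written. On that reading no power is lost, and widening the rule carries a type I cost.

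**Conclusion.** The gap in the text is certain: as written, normalising a variable can score worse than partly improving it, on the primary endpoint. Its frequency is unknown, and it is nil under the ordered reading. The documents do not show that anyone will score patients literally, and they support no estimate of lost power; the figures above are illustrations on assumed shares. The error runs one way, since the literal wording can lose responders but cannot create false activity. With 0 versus 1 of 10 and 2 versus 3 of 20 as cut-offs, one such patient is enough to change the decision, so the rule should be settled in writing.

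**What to change.** Add to the cPR row of Table 2 that, for WBC, peripheral-blood precursors, marrow blasts and spleen by sonography, the vPR requirement is met once the stated vPR reduction is reached, whether the value is still above the vCR range or already within it. Add that vCR of extramedullary disease counts towards cPR. Leave platelets, palpable spleen and the Table 1 bands unchanged.

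Say openly what this does not do. It removes the inversion, but normalisation with less than the minimum fall stays uncredited: WBC 25 to 14 (−44%) or marrow blasts 6% to 4% (−33%). The simpler alternative, vPR or vCR in at least one variable, would credit these, and also small changes such as platelets 99 to 101 or marrow blasts 5% to 4%.

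Apply the rule to all patients, including those already enrolled. Fix it without reference to accrued responses, which needs care in an open-label single-arm trial, and obtain DSMC approval (Section 12.2). Report the literal wording as a sensitivity analysis.

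The cost is two sentences and one extra analysis. The downsides are a small departure from the consensus wording, a possible rise in type I error, earlier first-response dates (and so longer durations) for some patients, and a possible effect on when the conditional odd-cycle marrow is triggered. Continuation of therapy depends on absence of progression, which the change does not touch.

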APPENDIX V: DETERMINATION OF PATHOGENICITY

Variants will be determined as pathogenic, likely pathogenic, variants of uncertain significance, likely benign or benign. A combination of assessments are used to determine the classification of each variant in accordance with the “Standards and guidelines for the interpretation of sequence variants: a joint consensus recommendation of the American College of Medical Genetics and Genomics and the Association for Molecular Pathology”.⁴⁷

Single nucleotide polymorphisms (SNPs): Variants are cross referenced in databases including:

dbSNP <https://www.ncbi.nlm.nih.gov/projects/SNP/>
ExAC <http://exac.broadinstitute.org/>
1000 genomes project. <http://www.internationalgenome.org/>

In silico prediction: Variants are assessed for pathogenicity using:

Mutation Assessor <http://mutationassessor.org/r3/>
SIFT <http://sift.jcvi.org/>
Polyphen. <http://genetics.bwh.harvard.edu/pph/data/>

Conservation: Variants are assessed using GERP (<http://mendel.stanford.edu/SidowLab/downloads/gerp/>) to assess for conservation amongst species.

Cancer Databases: Variants are cross-referenced in COSMIC (<http://cancer.sanger.ac.uk/cosmic>), and cBioPortal (<http://www.cbioportal.org/>) and assessed for prior evidence of pathogenicity.

Tumor-Normal: The allelic frequency for each variant is determined in both a tumor and a normal sample.

